10.2 ECOG performance status

ECOG performance status is an additional efficacy assessment performed in Part B of this study and is defined in [Table 10-1](#).

Table 10-1: ECOG Performance Status Scale

Grade	ECOG performance status scale
0	Fully active, able to carry on all pre-disease performance without restriction
1	Restricted in physically strenuous activity but ambulatory and able to carry out work of a light or sedentary nature (e.g. light housework, office work)
2	Ambulatory and capable of all self-care but unable to carry out any work activities. Up and about more than 50% of waking hours
3	Capable of only limited self-care, confined to bed or chair for more than 50% of waking hours
4	Completely disabled. Cannot carry out any self-care. Totally confined to bed or chair
5	Dead

ECOG=Eastern Cooperative Oncology Group.

ECOG performance status will be listed by treatment group at each visit for the SS.

ECOG performance status will be summarized as an ordinal categorical variable using frequency counts and percentages. Shift tables for the change from Baseline in each grade will be summarized by visit.

11. OTHER ANALYSES

Not applicable.

13. APPENDICES

13.1 SMQ algorithm for identification of anaphylactic reactions

Based on MedDRA® Version 25.1, the SMQ=‘Anaphylactic reaction’ consists of 3 parts:

1) A **narrow search** containing PTs that represent core anaphylactic reaction terms:

Category A

Anaphylactic reaction	Dialysis membrane reaction
Anaphylactic shock	Kounis syndrome
Anaphylactic transfusion reaction	Procedural shock
Anaphylactoid reaction	Shock
Anaphylactoid shock	Shock symptom
Circulatory collapse	Type I hypersensitivity

2) A **broad search**:

Category B

Acute respiratory failure	Laryngospasm
Asthma	Laryngotracheal oedema
Bronchial oedema	Mouth swelling
Bronchospasm	Nasal obstruction
Cardio-respiratory distress	Oedema mouth
Chest discomfort	Oropharyngeal oedema
Choking	Oropharyngeal spasm
Choking sensation	Oropharyngeal swelling
Circumoral oedema	Pharyngeal oedema
Cough	Pharyngeal swelling
Cough variant asthma	Respiratory arrest
Cyanosis	Respiratory distress
Dyspnoea	Respiratory failure
Hyperventilation	Reversible airways obstruction
Irregular breathing	Sensation of foreign body
Laryngeal dyspnoea	Sneezing
Laryngeal oedema	Stridor

Swollen tongue	Tracheal oedema
Tachypnoea	Upper airway obstruction
Throat tightness	Vaccine associated enhanced respiratory disease
Tongue oedema	
Tracheal obstruction	Wheezing
Category C	
Allergic oedema	Oedema
Angioedema	Oedema blister
Circumoral swelling	Periorbital oedema
Erythema	Periorbital swelling
Eye oedema	Pruritis
Eye pruritis	Pruritis allergic
Eye swelling	Rash
Eyelid oedema	Rash erythematous
Face oedema	Rash pruritic
Flushing	Skin swelling
Injection site urticaria	Swelling
Lip oedema	Swelling face
Lip swelling	Swelling of eyelid
Nodular rash	Urticaria
Ocular hyperaemia	Urticaria papular
Category D	
Blood pressure decreased	Cardiovascular insufficiency
Blood pressure diastolic decreased	Diastolic hypotension
Blood pressure systolic decreased	Hypotension
Cardiac arrest	Hypotensive crisis
Cardio-respiratory arrest	Post procedural hypotension

Note that if the MedDRA® version is increased from 25.1 during the study, any changes to the terms in the above categories should be applied.

The following **algorithmic approach** will be applied: A or (B and C) or [D and (B or C)], i.e.

If a participant has a TEAE which codes to a PT included in Category A, then the event will be flagged as an anaphylactic reaction. Note that participants with a TEAE coded to a PT='Type 1

hypersensitivity' will also be flagged as having a hypersensitivity reaction as this PT is also included in the Category A narrow search for the 'Hypersensitivity' SMQ.

OR

If a participant has a TEAE which codes to a PT included in Category B **AND** has a TEAE which codes to a PT included in Category C, **and both TEAEs have the same start date**, then both events will be flagged as anaphylactic reactions.

OR

If a participant has a TEAE which codes to a PT included in Category D **AND** has (either a TEAE which codes to a PT included in Category B **OR** a TEAE which codes to a PT included in Category C), **and both TEAEs have the same start date**, then both events will be flagged as anaphylactic reactions.

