- If the onset/start date is completely missing then the onset/start date will be imputed to the date of first dose of UCB6114 and therefore, for AEs, the event will be regarded as treatment-emergent and, for medications, the medication will be classified as concomitant.

The following rules will be applied to partial end/stop dates:

- If only the month and year are specified, then the last day of the month will be used;
- If only the year is specified, then December 31 of the known year will be used;
- If the stop date is completely unknown, the stop date will not be imputed.

Note that the start date or stop date of a prior medication (partial or otherwise) should not be imputed past the Screening date - 1.

In addition to onset and stop dates, the onset and end times of AEs occurring on the day of UCB6114 infusion will be collected on the eCRF. Onset and end times may also be recorded for other AEs that do not occur on the same day as the UCB6114 infusion. The duration of AEs with onset and end times will be calculated in days and hours:minutes (hh:mm) as:

$$\text{Duration of AE} = \text{End Date and Time} - \text{Onset Date and Time}$$

In cases where only the onset and stop dates are recorded for an AE, the duration of an AE will be calculated in days as:

$$\text{Duration of AE} = (\text{Stop Date} - \text{Onset Date}) + 1$$

Note that for participants who have an AE which starts and stops on the same day, but with only a start time or only a stop time recorded, it will be assumed that their AE started from 00:00 (if no start time is recorded) and ended at 23:59 (if no stop time is recorded) on that day.

If the date of a participant's initial diagnosis is incomplete, it will be imputed to the most recent feasible date for the calculation of time since initial diagnosis as follows:

- If only the day is missing, it will be imputed to the last day of the known month;
- If the day and month are missing, it will be imputed to December 31 in the known year;
- If the date of initial diagnosis is completely missing, then time since initial diagnosis will not be calculated.

The above date imputation rules will be applied to partially missing stop dates of a participant's last prior anti-cancer systemic therapy as well as partially and completely missing dates of progression/relapse on last prior anti-cancer systemic therapy.

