8.2.2 Infusion-related reactions

Infusion-related reactions are defined as hypersensitivity reactions, anaphylactic reactions and cytokine release syndrome with onset within 24 hours after the start of an infusion of UCB6114.

All potential infusion-related reactions will be identified programmatically and will then undergo medical review for confirmation based on participant characteristics and other signs and symptoms. The final assessment from the medical review will be used in the programming to ensure that all infusion-related reactions are flagged correctly in the listings and included in the relevant summaries.

Hypersensitivity reactions will be programmatically identified as any TEAE with a PT from both a narrow and broad scope search of category A terms of the ‘Hypersensitivity’ SMQ.

Anaphylactic reactions will be programmatically identified using an algorithmic approach based on the ‘Anaphylactic Reaction’ SMQ. Further details on this algorithm are given in [Section 11](#). Note that if the MedDRA® version is increased from 25.1 during the study, any changes to the terms included in the ‘Anaphylactic Reaction’ SMQ should be applied.

Cytokine release syndrome will be programmatically identified as any TEAE with a PT of ‘Cytokine release syndrome’ from the broad scope search of category A terms of the ‘Hypersensitivity’ SMQ. Since this disorder is characterized by fever, headache, tachycardia, hypotension, rash, tachypnoea and/or hypoxia, a further medical review of participants with these events occurring within 24 hours after infusion of UCB6114 will be performed to confirm any further infusion-related reactions.

Note that any other AEs (i.e. not identified as infusion-related reactions using the rules above) which result in a temporary interruption or permanent discontinuation of a UCB6114 infusion will not be considered as an infusion-related reaction.

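### Section 13.1 pairs the component events of an anaphylactic reaction by calendar date, so a pair split by midnight inside the 24-hour window of Section 8.2.2 is not flagged as potential anaphylaxis

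*SAP*

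**What the plan says.** The ONC001 SAP document contains separate plans for Part B and Part C; on this point they have the same rules.

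- **Definition (8.2.2).** Infusion-related reactions comprise hypersensitivity, anaphylaxis and cytokine release syndrome "with onset within 24 hours after the start of an infusion of UCB6114" (Part B wording; Part C is equivalent).
- **Order of steps (8.2.2).** "All potential infusion-related reactions will be identified programmatically and will then undergo medical review for confirmation". The program is the screen and the reviewer decides.
- **Algorithm (13.1).** A Category A term counts alone: "then the event will be flagged as an anaphylactic reaction". The other two branches, B with C and D with B or C, carry a further condition: "and both TEAEs have the same start date". The one-line formula above them, which begins "A or (B and C) or [D and (B or C", has no date condition; the explanatory text adds it.
- **Onset times (4.2.3).** "the onset and end times of AEs occurring on the day of UCB6114 infusion will be collected on the eCRF". For other days a time may be recorded but is not assured.

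**The concern.** A window of 24 hours from the start of an infusion covers two calendar dates unless the infusion starts exactly at midnight. Section 13.1 nevertheless asks that both component events carry the same date. A respiratory event late in the evening and a skin event shortly after midnight can both meet the definition in 8.2.2 and still fail the pairing rule.

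Because the medical review comes second and can reject false positives, the programmed step gains little from being narrower than the definition it serves. What is at stake is whether such a pair reaches the reviewer as a possible anaphylactic reaction. No later step in either SAP restores a split pair under that label.

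**Working it through.** **Inputs.** The 24-hour window comes from 8.2.2 and the same-date condition from 13.1. The SAP gives no infusion clock times and no onset distribution, so every clock time and percentage below rests on an assumption.

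**Step 1: the rule applied to two pairs.** Assume an infusion starting at 14:00 on Day 1, with one Category B and one Category C event.

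| Pair | Onsets | Hours from infusion start | Gap | Same date | Flagged |
|---|---|---|---|---|---|
| Split by midnight | Day 1 23:30, Day 2 00:30 | 9.5 and 10.5 | 1 h | No | No |
| Both on the next date | Day 2 00:30, Day 2 13:30 | 10.5 and 23.5 | 13 h | Yes | Yes |

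Both pairs lie inside 24 hours. The closer pair is dropped and the more widely spaced pair is kept. The date match is therefore not a test of closeness in time.

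**Step 2: how often a pair would be split, uniform onsets.** Let h be the infusion start hour and f = (24 - h)/24 the share of the window on the infusion date. For two independent uniform onsets, P(different dates) = 2f(1 - f).

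| Start | f | 2f(1 - f) |
|---|---|---|
| 09:00 | 0.625 | 0.469 |
| 10:00 | 0.583 | 0.486 |
| 12:00 | 0.500 | 0.500 |
| 14:00 | 0.417 | 0.486 |
| 16:00 | 0.333 | 0.444 |

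**Step 3: clustered onsets.** Here the time to first onset and the gap to the second are exponential (simulation, 1,000,000 draws per setting), keeping only pairs whose second onset is within 24 hours.

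| Mean time to first onset | Mean gap | Split, 10:00 start | Split, 14:00 start |
|---|---|---|---|
| 1-3 h | 0.5-2 h | 0-1.7% | 0-5.8% |
| 1-3 h | 6 h | about 10-15% | about 21-29% |
| 6-12 h | 0.5-2 h | about 1-7% | about 2-10% |
| 6-12 h | 6 h | about 20-23% | about 30-31% |

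The denominator throughout is qualifying pairs inside the window, not participants.

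**Step 4: untimed events.** For an infusion at 11:00 (assumed), an event dated the next day with no time could start as late as 23:59, which is 36 h 59 min after the infusion start. A missing time on the next date therefore cannot simply be read as inside 24 hours.

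**The case against.** The best case for the plan has five parts.

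1. *The two rules do different jobs.* One ties an event to an infusion; the other ties two events into one episode, using the field that is always available. This is fair as far as it goes, and the SAP does not contradict itself outright. But Step 1 shows that the date match serves the second job poorly. The SAP also already works with onset times elsewhere: 3.2.2 derives TEAE time from infusion start, and 8.2 assigns period of onset by date and time.
2. *There are other routes to review.* Category A terms need no partner. The Hypersensitivity search takes single terms with no date condition. The cytokine-release review covers hypotension, rash and tachypnoea, among others. This stands in part. That review does not name dyspnoea, wheezing, bronchospasm or throat tightness, which are Category B terms. The Hypersensitivity term list is not reproduced, so its coverage cannot be checked here.
3. *No planned output isolates anaphylaxis.* Section 8.2 tabulates infusion-related reactions, and the AE listing flags those. This stands: losing the anaphylaxis label alone changes no listed table. It matters where a component does not reach review by another route.
4. *The size may be trivial.* If reactions come early after daytime infusions, few pairs straddle midnight. This also stands. A reader might note that 38% to 58% of the window falls on the next date for starts between 09:00 and 14:00 (9/24 and 14/24) and take that as a miss rate. It is not one, because two events that both start on the next date share a date and are flagged.
5. *A looser rule admits noise.* Categories B and C include cough, sneezing, rash and oedema. This is true, and it is why the added pairs should be labelled potential and left to the reviewer.

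A reader might also infer that 8.2.2 formally shuts split pairs out. Its closing sentence does not say that: it concerns only other AEs "which result in a temporary interruption or permanent discontinuation of a UCB6114 infusion will not be considered as an infusion-related reaction".

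**Conclusion.** The point holds as a narrow one. In both SAPs the two paired branches of the anaphylaxis algorithm are stricter on timing than the definition of an infusion-related reaction, and a pair split by midnight inside the 24 hours is not flagged as potential anaphylaxis for review.

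The frequency cannot be known from the document. Under assumed clock times it runs from about 0-6% of qualifying pairs, if onsets are early and close together, to about 50% if they are independent and uniform. Each dose level has 3 to 9 evaluable participants, so one case weighs between 1/9 (11%) and 1/3 (33%) of a group. That is the weight of a single case, not an expected effect.

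The document does not support a reading that events disappear from safety reporting or that the primary endpoints are affected. Every component stays in the TEAE summaries and the AE listing, and DLT assessment does not use this flag. The correction is worth making because it is cheap and can change which events a reviewer sees.

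**What to change.** In Section 13.1 of both SAPs, replace the same-date condition in the two paired branches with: *start dates no more than 1 day apart, with both onsets within 24 hours after the start of the same UCB6114 infusion where onset times are available; where an onset time is missing, the pair is flagged as potential only and the 24-hour criterion is decided at the medical review already planned.*

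This loses no reportable case, since a same-date pair outside 24 hours is not an infusion-related reaction under 8.2.2. Flagging untimed pairs as potential only avoids counting a late next-day event (Step 4), or an infusion-day event that began before the infusion, as confirmed.

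The cost is one sentence and one program condition per SAP, plus some additional potential cases for the reviewer. These are probably few, but the document gives no basis for a count. In the same edit, correct the cross-reference in 8.2.2: it sends the reader to Section 11, which is marked not applicable, while the algorithm is in 13.1.

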13.2 SAP Amendment 1 Changes

The main rationale for SAP Amendment 1 is to include details on the additional key derived and component exploratory variables required based on the results from the analyses of historical tumor biopsy samples in Part B. It was decided that these additional variables were needed to improve the interpretability of the test results received from the laboratory. This SAP amendment also provides some clarifications relating to the handling of data for the purpose of summarizing safety and exploratory anti-tumor activity endpoints.

The key changes are summarized in the table below (note that additional minor corrections and clarifications were also applied in this amendment but are not included in this table).

Section	Description of Change
1	The versions and dates of supporting study documentation were updated.
5.1	An update was made to the example illustrating the definition of a complete cycle of UCB6114.
7	TFD/TPI compliance calculation and corresponding definitions were updated.
8.1	The additional summary of the total number of doses of study treatment received was included.
8.2	Rules for handling missing relationship to study treatment for an adverse event were updated.
8.4.2	Clarification on the handling of triplicate ECG measurements was included.
9.1.2	Updates were added for more clarification on how C_{min} and C_{max} is to be derived.
9.2	Details on the analysis of the historical tumor biopsy samples was included together with rules for defining key and component derived variables based on the test results received from the laboratory. These variables were considered important for clearer interpretation of these results from data listings.

Section	Description of Change
9.3	A predefined fold-increase of 1.80 was included.
10.1.2	Rules for applying the protocol-defined window around the post-Baseline tumor assessments (scheduled and unscheduled) for the purpose of summarizing the investigator's overall tumor response assessment were included.
General	MedDRA® version number was updated to the latest version (25.1) throughout the document.

STATISTICAL ANALYSIS PLAN SIGNATURE PAGE

This document has been reviewed and approved per the Review and Approval of Clinical Documents Standard Operating Procedures. Signatures indicate that the final version of the Statistical Analysis Plan (SAP) or amended SAP is released for execution.

CTMS	clinical trial management system
DCR	disease control rate
DEM	data evaluation meeting
DES	DLT Evaluable Set
DLT	dose limiting toxicity
DOR	duration of response
ECG	electrocardiogram
ECOG	Eastern Cooperative Oncology Group
eCRF	electronic case report form
EMA	European Medicines Agency
ES	enrolled set
EudraCT	European Union Drug Regulating Authorities Clinical Trials
FAP	fibroblast activation protein
FDA	Food and Drug Administration
Gastric cancer	gastric adenocarcinoma
GEJ cancer	adenocarcinoma of the gastroesophageal junction
geoCV	geometric coefficient of variation

geoMean	geometric mean
hh:mm	hours:minutes
H & E	hematoxylin and eosin
HLT	high level term
IHC	immunohistochemistry
ICH	International Council for Harmonization
IM	invasive margin
iv	intravenous
IPD	important protocol deviations
LLOQ	lower limit of quantification
LLT	low level term
LVEF	left ventricular ejection fraction
MedDRA®	Medical Dictionary for Regulatory Activities
mFOLFOX6	modified FOLFOX 6 regimen (leucovorin 400mg/m ² on Day 1, 5-fluorouracil 400mg/m ² on Day 1 + 1200mg/m ² /day on Day 1 and Day 2, and oxaliplatin 85mg/m ² on Day 1)
MTD	maximum tolerated dose
mTPI	modified toxicity probability interval
n	number of study participants
NCI CTCAE	National Cancer Institute Common Terminology Criteria for AEs
NC	not calculable
NCS	not clinically significant
NEst	not estimable
NV	no value
ORR	objective tumor response rate
OS	overall survival
PCS	potentially clinically significant
PD	pharmacodynamic(s)
PDILI	potential drug-induced liver injury
PDS	pharmacodynamic set
PK	pharmacokinetic(s)
PKS	pharmacokinetic set
PFS	progression-free survival
PPS	per-protocol set
PR	partial response
PT	preferred term
PTEN	phosphatase and tensin homolog
Q2W	every 2 weeks
QTcF	QT interval corrected for heart rate using Fridericia's formula
RECIST	Response Evaluation Criteria in Solid Tumors
RP2D-F	recommended Phase 2 dose of UCB6114 when used in combination with mFOLFOX6
SAE	serious adverse event

SAP	statistical analysis plan
SD	stable disease
SDTM	Study Data Tabulation Model
SFU	safety follow-up
SI	International System of Units
SMAD4	mothers against decapentaplegic homolog 4
SMC	Safety Monitoring Committee
SoC	standard of care
SOC	system organ class
SS	safety analysis set
SSC	Study Steering Committee
TEAE	treatment-emergent adverse event
TEMA	treatment-emergent markedly abnormal
TFL	Table, Figure and Listing
TNM	TNM Classification of Malignant Tumors
TPS	tumor proportion score
UK	United Kingdom
ULN	upper limit of normal
US	United States
WHODD	World Health Organization Drug Dictionary

This document cannot be used to support any marketing authorization application and any extensions or variations thereof.

1. INTRODUCTION

The purpose of this statistical analysis plan (SAP) is to provide all information that is necessary to perform the required statistical analysis of the dose escalation (combination therapy) module (Part C) of study ONC001. It also describes the summary tables, figures and listings (TFLs) to be generated for Part C according to

Protocol amendment 6, dated 26 June 2023;

Electronic case report form (eCRF) (Clinical Data Management System [CDMS] postproduction change [CPPC] #14, version 23.0, dated 14 April 2023);

UCB's standards for TFL shells version 2023Q1;

Part A TFL shells, final version 2.4, dated 04 July 2023 (under development);

Part B and C Mocks draft version 1.3, dated 13 March 2023 (under development);

Part A, B and C List of TFLs (LoT) draft version 1.2, dated 04 July 2023 (under development);

UCB's Derivation of Efficacy Endpoints document, version 0.6, dated 21 January 2022.

Unless specified in the sections below, Part C of the study will be analyzed as described in the most recent version of the protocol. If a future protocol amendment necessitates a substantial change to the analysis of the Part C study data, this SAP will be amended accordingly. In addition, if the methodology for the analysis of key study endpoints must be modified or updated prior to the final database lock for Part C of this study, a SAP amendment will be required. Protocol amendments that do not affect the statistical analysis will not necessitate an amendment to the SAP. If, after database lock, additional analyses are required to supplement the planned analyses described in this SAP, these changes will be described in the clinical study report (CSR) together with the associated rationale.

Note that there may be a number of data cut-offs defined prior to the final database lock for Part C due to the regulatory safety reporting requirements for this study.

The content of this SAP is compatible with the International Council for Harmonization (ICH)/Food and Drug Administration (FDA) E9 Guidance (ICH-E9).

UCB is the Sponsor and ICON PLC is the contract research organization (CRO) for this study.

